Group Intervention (total expected N = 90 (approximately 10 subjects at each site):

The DWW group intervention will consist of groups of approximately 5 subjects who meet together for 16 weeks, for two hours each week. Group meetings will be held virtually on Zoom.

A trained, deaf, ASL-fluent DWW counselor will lead the sessions. We estimate that up to 18 groups will be established during the study period, with each site running two intervention groups (5 subjects in each Zoom group). As we match subjects' and counselors' schedules, our intervention group sizes may range slightly in size. Subjects will be encouraged to continue with the same group throughout the 16 week program, to take best advantages of social interactions and group dynamics.

Selected sessions of the DWW Curriculum are included in this application; select counselor lesson plans/guides and counselor powerpoint presentations are also included. Subjects will be asked to complete a daily food and physical activity diary during the course of the 16-week intervention (via the MyFitnessPal online app or MyFitnessPal website, or via the DWW Subject Food Diary uploaded in the application). Subjects will complete a food diary using MyFitnessPal, or a "calorie counter" book called "The Calorie King." Each intervention session will include group sharing and problem solving, discussion of a weight management topic, which may include watching a powerpoint presentation and/or ASL video; and a discussion on goal setting and action planning for the next week. A key principle of the DWW Curriculum is motivational interviewing, in which the counselor acts as a facilitator to: 1) help participants identify/recognize their own unhealthy behaviors, 2) help individuals build skills that will promote behavior change, and 3) help group members to support each other to make behavior changes. The Curriculum includes group exercise activities ("Do It!"), experiential learning activities ("Try It!" such as learning how to read a nutrition label or modify a recipe to make it healthier), and group activities related to food preparation or encouraging of trying new recipes and healthy foods ("Taste It!").

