At weeks 6, 11, and 16, each subject receives a Personal Feedback Report [see template included with the curriculum] which reviews their physical activity and food consumption diaries and their weight changes. By the end of the 16-week curriculum, each individual will have approximately 32 hours of group contact time.

During the DWW 16-week intervention, each enrolled subject will be provided a scale for them to keep at home. They will use the scale to report their weight during 16-weeks intervention, 6-month maintenance period, and 6-mth and 18-mth follow up appointments.

Over the course of the 16 week intervention, subjects will be able to earn points for attendance, completeness of their food and physical activity diary, for including calorie counts on at least 6 days per week, and for meeting physical activity requirements for the week. Subjects will be able to redeem these points (called "Wisebucks") at three different sessions (sessions 6, 11, and 16) for a variety of items including water bottles, adjustable measuring spoons, and other prizes related to the purpose of DWW.

The group maintenance phase starts immediately after the 16-week intervention, and consists of two meetings of the original group via Zoom; one at month 3 of the 6-month maintenance period and one at month 6 of the 6-month maintenance period. This will again consist of review of self-monitored diet and physical activity, problem solving and goal setting/action planning for their long-term program. Group attendees will be encouraged to interact with their group members during the intervention and maintenance phases. Each person will receive videophone or Zoom calls/reinforcements during each month of the 6-month maintenance

period. Counselors will also email participants bi-weekly to check in with participants and provide additional support.

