The individual-level analyses will be carried out using paired t-tests to examine significance of differences in weight between baseline and the remaining data collection points. Other variables associated with individual outcomes of body weight will be identified using univariate analysis of correlation analysis or tests for multiple group comparison. Heterogeneity among sites can be explored by marginal analysis and model-based conditional analysis. Multiple regression analyses, including analysis of covariance (ANCOVA), will be based on generalized linear models (GLM), specifically for this project, including multiple linear regression models for continuous outcomes and logistic regression for dichotomous outcomes. Random effects can be incorporated in GLMs to account for correlation among repeated measures. Several least-squares and likelihood based methods, such as the Pearson's chi-squared test, Hosmer-Lemeshow test, and likelihood ratio test can be used to test the lack of fit or violations of assumptions of GLMs. In case of high-dimensional data in different scales, standardization will be applied before model fitting and variable selection. Variable selection approaches using AIC or BIC criteria will be used to select the significant predictors. Penalized-based variable selection procedures such as LASSO or SCAD may be used to overcome the drawbacks of ad-hoc methods of stepwise, best subset selection, etc. Missing (drop-out) data will be handled by appropriate statistical methods, which include maximum likelihood and/or direct maximum likelihood inverse probability weighting, and multiple imputations.

Secondary analyses will be carried out using paired t-tests to examine significance of differences in weight, Block dietary scores and IPAQ physical activity scores between baseline and the remaining data collection points for each group. Similarly, the costs of interventions will be analyzed. Finally, other variables associated with individual outcomes of change in body weight, Block score, and IPAQ score will be identified using univariate analysis as described previously. For age, gender, and all baseline variables associated with outcomes at the $P < .10$ level of significance, multivariate linear regression analyses will be performed to adjust for possible confounders.

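### Paired t-tests on participant-level change ignore Zoom-group clustering, so their standard errors are too small if changes correlate within groups

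*Combined protocol and SAP*

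**What the plan says.** In Section III, Data Analysis, the general statement is "The individual-level analyses will be carried out using paired t-tests to examine significance of differences in weight between baseline" and later visits. The secondary analyses are then specified: "Secondary analyses will be carried out using paired t-tests to examine significance of differences in weight, Block dietary scores and IPAQ physical activity scores". That sentence ends by saying the tests are done per group, without defining group in this single-arm study. Secondary Outcomes #1 to #3 are each an overall mean change from baseline to 6 months in fruit and vegetable servings, physical activity, and weight (the last only for BMI above 24.9).

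The Group Intervention subsection expects 90 participants in groups of about 5: "We estimate that up to 18 groups will be established during the study period, with each site running two intervention groups". On staying together it says: "Subjects will be encouraged to continue with the same group throughout the 16 week program, to take best advantages of social interactions and group dynamics". The counselor is also to "help group members to support each other to make behavior changes". For the later period the plan adds: "Group attendees will be encouraged to interact with their group members during the intervention and maintenance phases". A further 18 participants are expected to be treated one-on-one by a research-team counselor rather than the site's counselor.

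Two nearby provisions touch on correlation: "Random effects can be incorporated in GLMs to account for correlation among repeated measures", and "Heterogeneity among sites can be explored by marginal analysis and model-based conditional analysis".

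**The concern.** The paired t-test standard error is correct only if one participant's change says nothing about another's. Here, members of a Zoom group share a counselor, two hours of sessions a week for 16 weeks, and encouragement to influence one another. A plan that intends peer influence should not test its results as if there were none.

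The two provisions do not repair this. The random effects are optional and address repeated measures within a person. The site analysis is optional, concerns sites rather than Zoom groups, and leaves the t-test standard errors unchanged.

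At stake are the p-values and intervals for the health outcomes under Aim 4. With no control arm, each of these results rests on one mean change and its standard error.

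**Working it through.** **Inputs from the documents**
- 108 participants (Section II, item 1).
- 90 in up to 18 groups of about 5 (Group Intervention).
- 18 treated one-on-one, about 2 at each of nine sites (Option of 1:1 intervention).
- Up to 10 participants in one YMCA group (Modification July 13, 2023).

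The head count reproduces: 18 × 5 + 9 × 2 = 90 + 18 = 108.

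**Assumed, because the documents are silent**
- ICC of change within a group: 0.01, 0.05 or 0.10.
- Two-sided 5% level.
- Full enrolment.
- One-on-one participants independent of everyone else.

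**Formula.** For cluster sizes m with total N, the variance of the mean change is inflated by DEFF = 1 + ICC × (Σm²/N − 1). The true standard error exceeds the t-test's by a factor of about √DEFF. Type I error is about 2 × [1 − Φ(1.96/√DEFF)].

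**Main case.** Σm² = 18 × 25 + 18 × 1 = 468, and 468/108 = 4.33, so DEFF = 1 + 3.33 × ICC.

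| ICC | DEFF | √DEFF | Type I error, formula | Type I error, simulated |
|---|---|---|---|---|
| 0.01 | 1.033 | 1.017 | 5.4% | 5.4% |
| 0.05 | 1.167 | 1.080 | 7.0% | 7.1% |
| 0.10 | 1.333 | 1.155 | 9.0% | 8.9% |

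The simulated column uses 100,000 trials per setting with normal changes, a random group effect and no true mean change.

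**Variants** (simulated, ICC 0.01/0.05/0.10)
- One YMCA group of 10: Σm² = 16 × 25 + 100 + 18 = 518, so DEFF = 1 + 3.80 × ICC; 5.5/7.1/9.5%.
- The 90 grouped participants alone: DEFF = 1 + 4 × ICC; 5.4/7.4/9.6%.
- About 20% dropout (18 groups of 4 plus 14 one-on-one, N = 86): 5.4/6.4/8.0%.
- Half enrolment (9 groups of 5 plus 9 one-on-one, N = 54): 5.4/7.0/8.9%.
- Secondary Outcome #3, assuming 63 eligible (18 groups of 3 plus 9 one-on-one): Σm² = 162 + 9 = 171, so DEFF = 1 + 1.71 × ICC; 5.2/5.9/7.0%.

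**If correlation acts at site level**
- Sites taken as random, one-on-one participants unclustered: Σm² = 9 × 100 + 18 = 918, so DEFF = 1 + 7.5 × ICC; 5.8/9.4/13.8%.
- Sites random, all 12 participants per site clustered: DEFF = 1 + 11 × ICC; 6.3/11.5/17.5%.
- Inference limited to the nine named partners: site adds no inflation (4.9/4.8/4.3%).

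**Check of the remedy** (ICC 0 to 0.10 unless stated)
- CR2 with Satterthwaite degrees of freedom, by Zoom group: 5.0–5.1% (23.9 df); 4.8–5.1% with one group of 10 (21.5 df); 5.0–5.1% in the assumed BMI subset (22.2 df).
- The same analysis by group when sites are in fact random: 5.5/7.2/8.9% at ICC 0.01/0.05/0.10, so it does not protect against site-level correlation.
- CR2 by site, one-on-one participants kept in their site (8 df): 5.0–5.1% at ICC 0.01 to 0.10.
- Mixed model with a random group effect and Kenward-Roger df (40,000 trials): 3.3–4.6%, so conservative.

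**The case against.** The strongest reply is that little depends on this. The primary outcomes concern implementation, the protocol treats effectiveness as shown in earlier trials, and no stated decision uses these p-values. The size rests wholly on an assumed ICC: at 0.01 the excess is negligible, and if low enrolment also shrinks the groups (3 per group plus 18 one-on-one) type I error is only 5.1/5.7/6.9%. All of this stands. It limits the weight of the point without removing it.

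The target is also less clear-cut than it seems. The analysis text tests weight differences, whereas Secondary Outcome #3 is percentage change in those with BMI above 24.9. Applying the paired t-test to that endpoint is a reasonable inference, not something the plan states.

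The undefined per-group wording might mean delivery format. The one-on-one test would then have no Zoom-group clustering, and the test on the 90 grouped participants would show slightly more inflation (7.4% rather than 7.1% at ICC 0.05). If it means each Zoom group, each test has about 5 people and does not give the overall mean change that the outcomes define. Neither reading settles the matter.

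Finally, one counselor may lead both groups at a site, and clustering by Zoom group would miss that correlation. This is correct, and it is why a site-clustered analysis belongs alongside the group-level one.

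**Conclusion.** The concern holds. The planned tests assume independence that the intervention is designed to break, and nothing in the plan changes their standard errors. Under Zoom-group clustering at full enrolment, a nominal 5% test has a true level of about 5.4% to 8.9% for ICCs of 0.01 to 0.10. It is lower in the assumed BMI subset (5.2% to 7.0%). Figures as high as 17.5% arise only if sites are regarded as random and one-on-one participants share the site effect. With zero ICC there is no inflation.

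The ICC, the alpha and the subset size are assumptions. The effect is modest and confined to the precision and p-values of secondary outcomes, but it is cheap to correct and should be corrected.

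**What to change.** **Change to make**
- Keep the mean-change estimate. Replace the paired t-test standard error with a CR2 cluster-robust one by Zoom group, with Satterthwaite degrees of freedom and each one-on-one participant as a cluster of one. A random-group mixed model with Kenward-Roger df is an acceptable but conservative alternative.
- Report the same analysis clustered by site as a sensitivity analysis, keeping one-on-one participants in their site. Treating them as singletons there gave 5.3–7.4% if they do share the site effect.
- State whether inference is to the nine partners or beyond them, state the alpha, define what group means in the secondary-analysis sentence, and report the estimated ICC.

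**Cost**
- SAP wording, a few lines of code, and a Zoom-group identifier in the participant dataset. Counselors already enter weekly data by participant, and Primary Outcome #2 is a percentage of groups, so groups must already be tracked.
- Fewer degrees of freedom. With about 24 df by group, intervals are about 4% wider at ICC 0 (critical value 2.06 against 1.98). At half enrolment it is about 11.5 df and 9% wider. By site, with equal sites, it is 8 df and 16% wider (2.31 against 1.98).
- If only the nine partners are of interest and they truly differ, the group-level analysis is conservative (2.3–4.6%).

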The NCDHR is unique in its capacity to collect and disseminate reliable and accurate health information for use with Deaf persons using ASL video. The research team has extensive cultural and linguistic competence working with deaf populations and translating surveys from English to ASL or English-based sign language. During its first funding cycle (2004-2009), NCDHR developed linguistically and culturally appropriate survey methods that provide an assessment of the health status of deaf populations (the Deaf Health Survey, see RSRB # 20189).⁷

The original Deaf Weight-Wise Study (see RSRB # 34096) was the core research project for the second Prevention Research Center funding cycle (2009-2014), and was the first adequately powered trial of an evidence-based healthy weight/lifestyle intervention to be carried out in Deaf people.⁸ It is based on the University of North Carolina's Weight Wise program and was selected based on 1) its proven effectiveness with an underserved population, 2) having a scope and approach consistent with Deaf Community preferences, and 3) solely focused on weight and its related behaviors and showed significant and important changes in outcomes.⁹ It represented a pioneering effort to collect new health information and develop intervention tools in a very understudied and underserved minority group.

Deaf Weight Wise 2.0 (see RSRB #57628) was the core research project for NCDHR's third funding cycle (2014-2019), and was built on this research team's experience with the original Deaf Weight Wise trial for ages 40-70. DWW 2.0 was an adaptation of the original Deaf Weight Wise curriculum to suit ages 21-70, and evaluated the additional component of the one-to-one individual counseling intervention delivered remotely over videophone (like Skype/Zoom) in addition to the group intervention format.

This new Deaf Weight Wise implementation research proposed here will allow us to work with community partner organizations, to train them to implement DWW at their own sites/agencies. This will fulfill the goal of disseminating DWW broadly to Deaf communities. We will conduct research to study the process of implementation of DWW at each site. This advances DWW along the translational spectrum to ensure that DWW is not only a research project, but becomes a sustainable, community-based program.

II. CHARACTERISTICS OF THE RESEARCH POPULATION

- 1 **Number of subjects.** 108.
- 2 **Gender of Subjects.** Subjects of all genders will be included.

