- 7 **Vulnerable Subjects.** There are no special classes of individuals who may be considered vulnerable subjects that are targeted for enrollment in this study. Specific modifications have been made to make this study culturally and linguistically appropriate for use with Deaf participants. The researchers who have direct contact with study subjects, including the researchers who obtain informed consent and deliver the health intervention modules, will be fluent in ASL. This research includes the guidance of Deaf community advisory boards, whose members are deaf adult ASL-users. No children will be included in the research. Prisoners or institutionalized individuals will not participate in this research.

III. METHODS AND PROCEDURES

Overall study design

The overall design of the DWW Implementation Study will have up to nine sites hosting DWW in three cities. NCDHR is working with each site to establish a timeline for beginning the program; as each new site is added, we will upload their Letter of Cooperation as a Modification to our application (we will upload each Letter of Cooperation as an amendment, once they are received). It is important to note that these sites are NOT engaged in the research, as per the federal definition.

The total length of the full study at each site is about 18 months for individual participants (baseline and two follow-up data collection points). Interventions will consist of 16-week group counseling Zoom sessions led virtually by trained, ASL-fluent Deaf counselors. Following the

16-week intervention, subjects will enter a 6-month “maintenance phase” with less intense interventions. This study is by definition a single-arm interventional clinical trial; we will register this study on clinicaltrials.gov as required, and will submit a modification to enter the NCT number prior to conducting the study.

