Data management by the DWW counselor: During the DWW 16-week intervention, prior to each week's session, the group counselor will email each participant individually to ask for their weight and collect the summary/cover page of each participant's Food Diary (which summarizes daily caloric intake, daily exercise, and daily fruit and vegetable consumption for the previous week). The counselor will then enter this weekly data into a secure REDCap database that is managed by an NCDHR research coordinator. The research coordinator will monitor and analyze the weekly data from subjects including weight, attendance record (present or absent for that week), and Food Diary information, and will discuss any concerns with the research team and the PI.

Option of 1:1 (one-on-one) Zoom/Videophone intervention - (total expected N = 18 (approximately 2 subjects at each site):

Some circumstances may require that a participant receive the DWW intervention in a one-on-one format over zoom or videophone. Reasons for this may include but are not limited to:

- participant does not have a computer or laptop or device that allows for adequate participation in zoom; participant may be able to use their existing personal videophone only,
- participant is unable to participate effectively in a group setting,
- participant uses a different sign language or other forms of communication which require more intense instruction by the counselor.

If a participant is identified by the research team as needing a one-on-one intervention modality, a trained intervention counselor from this NCDHR research team will deliver the intervention to this participant (meaning, the counselor at the partner site will NOT be required to deliver the intervention one-on-one to these participants). We expect that up to 2 participants at each site may require this one-on-one intervention.

Training of DWW Counselors

DWW counselors who will deliver the intervention sessions will be deaf, sign-fluent, and may have a background in clinical, educational, or health-related fields. Partner sites will work with the NCDHR research team and NCDHR DWW Lead Counselors to identify a counselor(s) to work with the site to deliver the intervention to subjects.

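### The secondary paired t-tests are planned by an undefined 'group' in a single-arm study, which conflicts with secondary outcomes defined as one overall mean change to 6 months

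*Combined protocol and SAP*

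**What the plan says.** Under Overall study design the protocol states: "This study is by definition a single-arm interventional clinical trial". There is no comparator and so no treatment arm.

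Under Data Analysis, weight change is tested twice. The first participant-level paragraph plans paired t-tests of weight against each later visit, with no split. The secondary-analyses paragraph plans paired t-tests of weight, Block dietary scores and IPAQ scores "between baseline and the remaining data collection points for each group". What a group is for this purpose is not defined.

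The three listed secondary outcomes follow: fruit and vegetable servings, physical activity, and weight change as a percentage of baseline weight in participants with BMI above 24.9. Each is a mean change from baseline to 6 months, and none mentions groups.

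The Intervention Description offers several candidates for the word:
- Zoom groups: "We estimate that up to 18 groups will be established during the study period", with "5 subjects in each Zoom group".
- Delivery format: group sessions ("total expected N = 90 (approximately 10 subjects at each site") or one-on-one ("total expected N = 18 (approximately 2 subjects at each site").
- Site or city: "up to nine sites hosting DWW in three cities".

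**The concern.** An analyst following the secondary-analyses sentence would divide the sample and test each part. An analyst following the outcome list would produce one estimate per outcome. The two instructions give different results, and nothing says which governs. For Block and IPAQ the split sentence is the only test of mean change in the plan; their other mentions concern predictors and confounder adjustment.

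These outcomes serve Aim 4, which asks about participants' health-related outcomes. Reported by small group, they would appear as a scatter of imprecise results in which a few nominally significant ones could be picked out. No significance level or multiplicity rule is given for these tests. Because the unit is undefined, it could also be chosen after the data are seen.

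**Working it through.** **The plan's own sample size.** Nine sites × (10 group + 2 one-on-one) = 90 + 18 = 108, which agrees with "Number of subjects. 108". Nine sites × 2 groups = 18 Zoom groups, and 18 × 5 = 90.

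**Inputs.** From the documents: three outcomes in the disputed sentence; two follow-up visits (6 and 18 months, the last being 12 months for the final 10 YMCA participants); the unit counts above. Assumed, because the plan gives no figure: two-sided level 0.05, and a standardized mean change d (mean change divided by the SD of change).

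**Number of tests.** Tests = units × 3 outcomes × visits. Expected false positives = tests × 0.05, if every null hypothesis is true.

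| Meaning of group | Tests at 6 months | Expected false positives | Tests, both visits | Expected false positives |
|---|---|---|---|---|
| Zoom group (18) | 18×3 = 54 | 2.7 | 108 | 5.4 |
| Site (9) | 9×3 = 27 | 1.35 | 54 | 2.7 |
| Delivery format (2) | 2×3 = 6 | 0.3 | 12 | 0.6 |
| No split | 3 | 0.15 | 6 | 0.3 |

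That 108 tests equals the sample size of 108 is a coincidence.

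**Power.** For a paired t-test, power is the probability that a noncentral t variable with n − 1 degrees of freedom and noncentrality d√n exceeds the two-sided 5% critical value in absolute size.

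| n | Where it arises | d = 0.3 | d = 0.5 | d = 1.0 |
|---|---|---|---|---|
| 5 | one Zoom group | 8% | 14% | 40% |
| 10 | group participants at one site | 14% | 29% | 80% |
| 18 | all one-on-one participants | 23% | 52% | 98% |
| 90 | all group participants | 80% | 99.7% | over 99% |
| 108 | everyone | 87% | 99.9% | over 99% |

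With n=5, 80% power needs d of about 1.69. If only three people in a group contribute, through dropout or the BMI restriction, power at d = 0.5 is 8%.

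**Does clustering remove the gain from pooling?** With groups of 5 the design effect is 1 + 4 × ICC. The plan gives no ICC, so two values are assumed. At 0.05 the effective n is 90/1.2 = 75, and power is about 73% at d = 0.3 and 99% at d = 0.5. At 0.10 it is 90/1.4 = 64, with 66% and 98%. Pooling remains far better than testing groups of 5.

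**Who is left out.** One-on-one participants belong to no Zoom group. On that reading 18/108 = 17% of the sample enters none of these tests.

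**The case against.** The strongest reply is that nothing says the tests are run per Zoom group. The word has other uses in the protocol: racial groups, study groups in the monitoring text, tests for multiple group comparison, and older versus younger survey respondents. Delivery format is a plausible meaning and covers everyone, with only 6 tests at 6 months and ample power in the larger format. This stands. A reader might infer that the plan commits to 108 tests and will yield several false positives; the documents do not support that. The figure of 108 is an upper bound: it needs the Zoom-group reading and the final visit, which the listed outcomes do not use. The 5.4 false positives also need an assumed 5% level and every null true, so that figure cannot be combined with power figures that assume real effects in the same tests.

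Further points stand in part. Group size is approximate, and the July 2023 modification allows up to 10 in the YMCA group, so n=5 is not fixed. Low power depends on effect size: at n=5 it is 40% for d = 1.0 and 71% for d = 1.5. Weight already has an unsplit test, although that test is not limited to BMI above 24.9 as the listed outcome is.

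The plan's optional modelling does not settle the matter. Random effects may be added for repeated measures, not for clustering by group, and heterogeneity among sites may be explored, with no method fixed.

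**Conclusion.** The point holds as an inconsistency between the secondary-analyses sentence and the listed secondary outcomes. Under every by-group reading the sentence yields split tests, while the list calls for one mean change per outcome. Block and IPAQ are most affected, since they have no other planned test of mean change.

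The size depends on the reading: 6 to 54 tests at 6 months where 3 would do, and power in the smallest unit of 14% (Zoom group), 29% (site) or 52% (one-on-one format), against over 99% pooled at n=90. These figures assume a two-sided 5% level and d = 0.5, and precede any allowance for clustering, dropout or the BMI restriction. Which reading the authors intended cannot be settled from the documents. Only secondary, participant-level results are affected, so this should be corrected but does not threaten the study's main purpose.

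**What to change.** Delete the closing three words of the secondary-analyses sentence. State that each listed secondary outcome is estimated once, as the mean change from baseline to 6 months with a 95% confidence interval, over all eligible participants (BMI above 24.9 for weight). Use a model with a random intercept for intervention group, entering each one-on-one participant as their own cluster, or use cluster-robust standard errors. State the significance level and how multiplicity across the three outcomes is handled. Present Zoom-group, site and delivery-format results descriptively, without p-values.

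The cost is a short text amendment and a little more analysis work than a paired t-test. Intervals will be slightly wider than a plain paired t-test would give, because they allow for clustering. No additional data are needed.

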Official Title: Deaf Weight Wise: Community-engaged Implementation Research to Promote Healthy Lifestyle Change With Deaf American Sign Language Users

NCT Number: NCT05211596

Document Date: 7/13/2023

Deaf Weight Wise: Implementation Research
Study Protocol: RSRB # 5784
Rochester Prevention Research Center: National Center for Deaf Health Research

I. PURPOSE OF THE STUDY AND BACKGROUND

Purpose of the study

The purpose of the Deaf Weight Wise Implementation Study is to study with diverse partners the approaches and strategies that lead to successful implementation of Deaf Weight Wise (DWW), RPRC's evidence-based healthy lifestyle intervention for use with Deaf adult American Sign Language (ASL) users.

The study aims are:

Aim 1: Adapt and implement DWW with partner organizations at different sites in upstate NY.

Aim 2: Assess the factors influencing adoption, adaptation and maintenance of the DWW intervention components using mixed methods.

Aim 3: Perform economic modeling to assess the cost-benefit of DWW, and associations with contextual factors and implementation strategies.

Aim 4: Assess with DWW participants the health-related outcomes and intervention experiences, and the associations of those outcomes with fidelity to DWW intervention components and implementation strategies.

Implementation (site-level) hypothesis: Diverse community organizations will successfully implement DWW with their constituents.

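### AIC/BIC survivors are labelled significant predictors with no correction for selection, and the Aim 4 association analysis has no fixed model and no firm allowance for site

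*Combined protocol and SAP*

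**What the plan says.** All of the participant-level association methods stand in section III of the combined protocol and SAP, under Data Analysis. Two rules for choosing variables appear there, in separate paragraphs.

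- The first paragraph on modelling says: "Variable selection approaches using AIC or BIC criteria will be used to select the significant predictors". It adds that LASSO or SCAD may be used because ad-hoc selection has drawbacks.
- The paragraph on secondary analyses looks univariately for variables associated with change in weight, Block score and IPAQ score. For age, gender and "all baseline variables associated with outcomes at the $P < .10$ level of significance", it then says "multivariate linear regression analyses will be performed to adjust for possible confounders".

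On correlation, the plan allows random effects for repeated measures and says that heterogeneity among sites may be explored by marginal or conditional analysis.

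The question these methods must serve is in section I. Aim 4 covers participant outcomes and "the associations of those outcomes with fidelity to DWW intervention components and implementation strategies". The section names no Aim 4 model, no list of candidate predictors, no multiplicity rule, no validation step and no exploratory label.

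**The concern.** A variable kept because it fits the outcome well in a data set cannot be called significant on the strength of being kept. AIC and BIC rank models; they do not control an error rate at a chosen level. The plan nevertheless equates being kept with being significant, and it does so where Aim 4 needs an inferential answer.

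The second weakness is the unit of analysis. Attendance varies between participants, but an implementation strategy adopted by a site is shared by everyone recruited there. The information about such a factor comes from at most nine sites, not from about 100 people. The plan ties its random effects to repeated measures only and leaves site as something that may be looked at.

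At stake are the statements made about which participant characteristics, delivery features or strategies go with better outcomes. Future sites may act on these.

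**Working it through.** **Inputs from the documents.** Section II gives "Number of subjects. 108". Section III gives "up to nine sites hosting DWW in three cities", a group format with "total expected N = 90 (approximately 10 subjects at each site") and a one-on-one format with "total expected N = 18 (approximately 2 subjects at each site"). The total reproduces: 9 × 10 + 9 × 2 = 90 + 18 = 108. It is a capacity count; no power or error rate is stated for the predictor analyses.

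**Assumptions.** The documents give no number of candidates (k), dropout rate or intraclass correlation (ICC). I take k = 10 and 20, with 5 and 30 as outer values; n = 108, and n = 86 for 20% dropout (108 × 0.8 = 86.4); and ICC 0.02, 0.05 and 0.10.

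**Step 1: chance that one noise variable is kept.** A single extra term survives if its likelihood-ratio statistic exceeds the penalty.
- AIC: P(χ²₁ > 2) = 0.157.
- BIC at n=108: P(χ²₁ > ln 108) = P(χ²₁ > 4.68) = 0.030.

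**Step 2: chance that at least one of k is kept**, using 1 − (1 − p)^k for independent candidates.

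| k | AIC | BIC |
|---|---|---|
| 5 | 58% | 14% |
| 10 | 82% | 27% |
| 20 | 97% | 46% |
| 30 | 99% | 60% |

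**Step 3: simulation.** This used 2,000 runs per setting, all candidates noise, age and sex forced in, backward selection, n=108, and pairwise correlation 0 or 0.3.

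| k | AIC keeps at least one | mean number kept (AIC) | BIC keeps at least one |
|---|---|---|---|
| 10 | 85-87% | 1.9-2.0 | 30-32% |
| 20 | 98-99% | 4.0-4.3 | 52-53% |
| 30 | over 99% | 7.0-7.2 | 69-72% |

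At n=86 the pattern is the same: AIC 85% to over 99%, BIC 34-76% over k = 10 to 30. These rates are for one outcome, and the plan searches three.

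**Step 4: how much is selection and how much is plain multiplicity.** A full model with no selection has at least one p<.05 in 38-40% (k=10) and 58-60% (k=20). After AIC selection, at least one kept noise variable has p<.05 in 44-54% and 75-81%. After the P<.10 screen the figures are 25-38% and 29-61%, so the screen adds little or nothing to the unselected rate.

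**Step 5: site-level factor with site ignored.** With m = 10 per site the design effect is 1 + (m − 1) × ICC, and the nominal 5% test has an actual size of about 2 × P(Z > 1.96/√DE).

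| ICC | DE | 1.96/√DE | actual size |
|---|---|---|---|
| 0.02 | 1.18 | 1.80 | 7.1% |
| 0.05 | 1.45 | 1.63 | 10.4% |
| 0.10 | 1.90 | 1.42 | 15.5% |

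Simulations of 9 sites of 10 with an ordinary t-test agree (about 7%, 10% and 15%), while a test on site means stayed at about 5%.

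**The case against.** Several points on the other side are sound.

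- **The P<.10 rule.** A reader might infer that the screen and AIC/BIC form one pipeline whose survivors are all called significant. The documents do not say so. The screen covers baseline variables only and chooses adjustment covariates. Attendance and fidelity arise during delivery, so the screen does not select Aim 4's own exposures.
- **Screening as the cause of false p<.05 results.** A figure near 60% for 20 candidates is tempting to quote, but Step 4 shows that an unselected model gives about the same. It is ordinary multiplicity.
- **Adjustment for confounders in a single-arm study.** It is tempting to call this meaningless. The sentence follows one about variables associated with change, however, and confounding can affect such associations.
- **Independence of participants.** The plan does not declare that site will be ignored. It mentions exploring site heterogeneity by methods suited to clustered data. That text is optional and is not tied to any Aim 4 test, so Step 5 shows what happens if the option is not taken up. Site-level implementation measures are described in a separate protocol not available here.
- **BIC and penalised methods.** BIC at this sample size is stricter than 0.05 per variable. LASSO or SCAD may be used, but that commits to nothing, and a penalised fit alone does not yield valid p-values.

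What remains is the sentence that commits to AIC or BIC and names its result significant, and the lack of a fixed Aim 4 model with a site term.

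**Conclusion.** The point holds and is minor. A stated rule labels data-selected variables as significant without any error control, and it sits among the only participant-level methods available for Aim 4. Under AIC, at least one false predictor is close to certain once candidates number 10 to 20 (85-99%); under BIC it is 30-53%. Those figures rest on an assumed candidate count and on all candidates being noise; with 5 candidates they fall to 58% and 14%. The site-level figures of about 7%, 10% and 15% rest on assumed ICCs and on site being left out of the test.

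A reader might take this to undermine the trial's main results. It does not: both primary outcomes are site-level implementation measures, the three secondary outcomes are mean changes from baseline, and neither set uses variable selection.

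**What to change.** In the Data Analysis section:

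1. For Aim 4, specify one model per outcome in advance: baseline value, age, gender, attendance or fidelity, and a random intercept for site.
2. Test strategy factors that differ by site at the site level, for example on site means.
3. Report every variable found by the P<.10 screen, AIC/BIC or LASSO/SCAD as an exploratory estimate with a confidence interval, and delete the term for significant predictors.
4. Say whether the Aim 4 terms carry significance claims. One term tested at 5% on three outcomes gives 1 − 0.95³ = 14% if the tests are independent, so either apply Holm across them or label them exploratory too.

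This is a change of wording and needs no new data. The cost is that fewer variables can be claimed as predictors, and tests of strategy factors will rest on at most nine sites and so have little power.
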